5.5 Study Evaluations

All potential participants will be screened for eligibility as described above for inclusion/exclusion criteria using medical charts and collection of general history information related to cancer diagnosis, treatment, dysphagia treatment, and current swallowing problems. Once deemed eligible, the participants will then undergo evaluation to determine eligibility for RST that includes an MBSS with simultaneous respiratory recordings, completion of cognitive screen (MoCA) (Appendix), and questionnaire (MDADI) (Appendix).

If participants meet eligibility criteria to participate in RST as outlined above, each participant will undergo in-clinic RST sessions with an SLP. After the RST is completed, participants will undergo an MBSS with simultaneous recordings, completion of MDADI, and information about oral intake/diet tolerance (FOIS) (Appendix) for post-treatment measurements. Further, the participant will undergo these same procedures at 1-month, 3-months, and 6-months after experimental portion is completed.

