5.6 Data Analysis

Statistical Considerations. Specific Aim 1: Trial design. The primary objective of Specific Aim 1 is to demonstrate the clinical efficacy and durability of RST in participants with dysphagia with a history of OP HNC. A total of 88 participants will be [recruited and randomly assigned 1:1 to either RST (intervention arm) or control arm, given the crossover design of the study. We will use a stratified permuted block randomization scheme with random block sizes of 2 or 4 to balance important prognostic variables across the two trial arms. There will be 5 strata defined by treatment modality (radiation therapy alone, surgery alone, chemo-radiation therapy, surgery + post-operative radiation therapy, surgery + post-operative radiation therapy + adjuvant chemotherapy). The study statistician will maintain randomization lists and be responsible for randomizing consented participants. The study schema is depicted in Figure 8. The control arm will cross over to RST after visit 1 following data collection for evaluation of clinical efficacy.

Endpoint Definitions and Analysis Plans. The primary efficacy endpoint for Aim 1 is oropharyngeal swallowing physiologic metrics (MBSImp) and evaluated at: visit 0, defined as pre-RST for intervention subjects, and baseline for control subjects; and visit 1, defined as post-RST for intervention subjects or 4 weeks post-baseline evaluation for control subjects. We will compare changes in MBSImp physiologic function metrics in patients randomized to intervention versus control. Change in MBSImp physiologic function metrics will be compared using one-way analysis of covariance (ANACOVA), with trial arm as the main effect and adjustment for stratification variable of treatment type. If approximate normality is not satisfied, we will use generalized estimating equations (GEEs) with an identity link function and robust standard error estimator. Furthermore, the regression framework of GEEs will accommodate adjustment for stratification factor. Durability of response will be evaluated using ANACOVA or GEEs as described by comparing post-RST MBSImp physiologic function metrics to those obtained at 1-, 3-, and 6-month follow-up visits. We will further evaluate the modifying and confounding effects of sex, age, smoking status, COPD status, and pulmonary function.

[figure not shown]

Figure 7 Study schema for current proposal.

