Further, response durability will be evaluated using FOIS measures obtained at 1-, 3- and 6-months post-RST. Because control subjects cross over to RST at visit 1, FOIS measures collected at visit 1 for control subjects additionally will serve as their pre-RST FOIS measures (Figure 7). Clinical efficacy will be evaluated by comparing change in FOIS (Δ FOIS = FOIS_{visit1} – FOIS_{visit0}) in patients randomized to intervention versus control. Δ FOIS comparisons will be conducted using one-way analysis of covariance (ANACOVA), with trial arm as the main effect and adjustment for stratification variables. If approximate normality is not satisfied, we will use generalized estimating equations (GEEs) with an identity link function and robust standard error estimator, which accommodates valid inference in the presence of misspecification.^{103,104} Furthermore, the regression framework of GEEs will accommodate adjustment for stratification factors. Durability of response will be evaluated using ANACOVA or GEEs as described by comparing post-RST FOIS measurements to those obtained at the 1-, 3- and 6-months follow-up visits. In addition, we will model longitudinally collected FOIS scores as a function of time (measured as a categorical variable) using GEEs, with additional independent variables for stratification factors and pre-RST FOIS included in all models. Comparisons at individual time points will be performed using model-based linear contrasts with inference based on associated two-sided generalized score tests. We will further evaluate the modifying and confounding effects of sex, age, smoking status, COPD status, and pulmonary function. Secondary endpoints include MDADI summary scores, and respiratory-swallow phase patterns (binary measure classified as optimal versus non-optimal) collected at all time points. Analysis of MDADI scores will follow the approach used to analyze FOIS scores. Comparisons between visits 0 and 1 respiratory-swallow phase patterns will be performed using a Rao-Scott chi-square test, an approach that accommodates comparisons of proportions from paired data with Mantel-Haenszel-type adjustments for stratification factors.¹⁰⁵ GEE models of respiratory-swallow phase patterns will be similar to those described for FOIS measures but using instead a

logit or probit link function as appropriate for binary endpoints. Results for all endpoints will be summarized separately for males and females to assess differences by patient sex.

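### Durability of the primary MBSImP outcome lacks a defined repeated-measures analysis: a normality check decides whether within-person correlation is handled, and no benefit retained over pre-RST is estimated

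*Combined protocol and SAP*

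**What the plan says.** Section 5.6 (Data Analysis, Endpoint Definitions and Analysis Plans) makes durability part of the Aim 1 primary objective, beside efficacy. For the primary outcome the durability plan is one sentence: "Durability of response will be evaluated using ANACOVA or GEEs as described by comparing post-RST MBSImp physiologic function metrics". The comparators it names are the three follow-up visits at 1, 3 and 6 months.

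The method it refers back to is the efficacy analysis: "Change in MBSImp physiologic function metrics will be compared using one-way analysis of covariance (ANACOVA), with trial arm as the main effect", adjusted for treatment type. The alternative has a single trigger: "If approximate normality is not satisfied, we will use generalized estimating equations (GEEs) with an identity link function and robust standard error estimator".

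The later values come from the same people. Section 5.5 says that after RST "the participant will undergo these same procedures at 1-month, 3-months, and 6-months after experimental portion is completed". Controls cross over to RST after visit 1, so both arms have been treated by the time these values exist.

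For FOIS, Section 5.6 goes further: "In addition, we will model longitudinally collected FOIS scores as a function of time (measured as a categorical variable) using GEEs", with stratification factors and the pre-RST score in every model and linear contrasts at each time point. It applies the same approach to MDADI and a similar one to respiratory-swallow phase pattern. The Aim 2 statistical text (Sections 5.1 and 5.6) lists ANACOVA, GEEs and Rao-Scott tests together for MBSImP impairment rates, composites and time-course data, and refers back to Aim 1 for the methods.

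**The concern.** Three things are left open for MBSImP durability.

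- **Choice of method.** Whether repeated values on one person are treated as correlated depends on a distributional check. Normally distributed values from one person are still correlated.
- **The effect tested.** The model referred to has trial arm as its main effect. After cross-over, that compares people who had RST early with people who had it four weeks later. It does not ask whether benefit has been lost.
- **The estimand.** The only stated contrast is post-RST against follow-up. A difference near zero with a wide interval cannot separate retained benefit from a loss that the trial is too small to see. Nothing in Aim 1 estimates how far MBSImP at 1, 3 or 6 months remains better than before RST.

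At stake is the durability half of the Aim 1 objective. The randomized visit 0 to visit 1 efficacy comparison is not affected.

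**Working it through.** The plan states no power, alpha, margin or sample size for durability, so there is no figure to reproduce. The 95% power and two-sided alpha of 0.025 in Section 5.1 belong to the between-arm efficacy comparison.

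**Inputs**
- n = 36 completers: 40 randomized less the 10% attrition allowance in Section 5.1 (40 × 0.9). Section 5.6 also gives 88.
- Assumed, because the documents do not give them: within-person correlation ρ = 0.3, 0.5, 0.7; equal SD at each visit; two-sided alpha 0.05; true loss from post-RST to follow-up of d = 0.25 or 0.5 SD.

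**Formulas (SD units)**
- Correct SE of a visit contrast: √(2(1−ρ)/n). At n = 36: 0.197, 0.167, 0.129.
- SE if visits are stacked as independent rows: √(2/n) = 0.236.
- Ratio: 1/√(1−ρ).
- True size of the stacked test: 2Φ(−1.96 × ratio).
- Stacked power: Φ(d/SE − 1.96 × ratio), with SE the correct one. Example, ρ = 0.5 and d = 0.25: Φ(1.500 − 2.772) = 10%.
- Paired power: paired t test with non-centrality d/SE.

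| ρ | SE ratio | True size | 0.25 SD: stacked | 0.25 SD: paired | 0.5 SD: stacked | 0.5 SD: paired |
|---|---|---|---|---|---|---|
| 0.3 | 1.20 | 1.9% | 13–14% | 23% | 56–58% | 69% |
| 0.5 | 1.41 | 0.6% | 9–10% | 31% | 57–59% | 83% |
| 0.7 | 1.83 | 0.04% | 4–5% | 47% | 59–62% | 96% |

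The lower stacked value uses the t critical value on 70 df, the upper the normal one.

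**Sensitivity**
- With n = 88 and a 0.25 SD loss, paired power is 50%, 64% and 85%, and stacked power 35%, 33% and 28%.
- A simulation (n = 40, 1,000 runs per cell) added the pre-RST score as a covariate, which the described MBSImP model does not name. Stacked size was about 1%. Power for a 0.25 SD loss was 22% against 34% paired at ρ = 0.5, and 35% against 55% at ρ = 0.7. The gap narrows but remains.
- For an arm effect across four stacked visits the error runs the other way. The true SE is √(1+3ρ) = 1.38 to 1.76 times the reported one, giving a type I error of about 16% to 27%.

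**Anchor to the pilot.** In the preliminary-trial table (Section 2.0), laryngeal vestibular closure impairment fell from 78.2% to 55.5%. Take a participant-level binary outcome, n = 36, normal approximation and a paired variance of [p₁q₁ + p₂q₂ − 2ρ√(p₁q₁p₂q₂)]/n. The stacked test uses the pooled proportion.
- Half the benefit lost (55.5% to 66.85%): stacked 12%, 8%, 4%; paired 22%, 29%, 44%.
- All of it lost (55.5% to 78.2%): stacked 54%, 55%, 56%; paired 71%, 84%, 97%.

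**The case against.** The strongest reply is that the SE error is imputed. No section says that visits will be stacked as rows or that visit is a factor. The ANACOVA described analyses change, one value per participant. Applied to change from post-RST to a given follow-up visit, it handles the correlation. MBSImP components are ordinal with three to five levels, so the normality check may well fail and lead to the robust GEE. All of this stands: the SE error is conditional. It does not settle the point, because the change-score version with arm as main effect would test whether the arms differ in loss, not whether benefit is lost.

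A reader might also infer that the longitudinal GEE is promised for FOIS alone. It is not: Section 5.6 extends it to MDADI and phase pattern, and the Aim 2 text mentions MBSImP time-course data. One can argue that this reaches the FOIS model through the reference to Aim 1. But that sentence lists three methods without saying which applies to repeated visits.

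Another tempting reading is that the sponsor will treat a non-significant difference as durability. No section says so. What can be said is that no other criterion is given.

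Finally, small numbers explain part of the low power: even a correct paired analysis misses a 0.25 SD loss more often than not at n = 36. That is a reason to report intervals. A formal retention test would not rescue it. With an illustrative margin of half of a 0.5 SD benefit, n = 40 and one-sided 0.025, power is Φ(0.25/SE − 1.96) = 35% at ρ = 0.5 and 53% at ρ = 0.7.

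**Conclusion.** The point holds as a gap in specification. For MBSImP durability, the plan lets normality choose the method, points to an arm effect that does not answer the question after cross-over, and estimates no retained benefit over pre-RST.

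The numerical harm is conditional. If visits are analysed as independent rows, the SE of a visit contrast is 1.20 to 1.83 times too large and the true size about 2% or less. Power for a 0.25 SD loss is about 4% to 14% instead of 23% to 47%, and for a 0.5 SD loss about 56% to 62% instead of 69% to 96%. These figures rest on assumed ρ of 0.3 to 0.7, equal SDs, alpha 0.05 and 36 completers. They improve with 88 participants, and the stacked penalty shrinks if the pre-RST score is a covariate.

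The documents do not support saying that the planned standard errors are wrong outright, or that loss of benefit would usually be missed. The latter is true of a small or partial loss. A 0.5 SD loss, or complete loss of the pilot closure benefit, would be detected more often than not even by the stacked analysis.

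**What to change.** In Section 5.6, replace the MBSImP durability sentence with the longitudinal model already written for FOIS, used whatever the normality check shows:

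- Cluster on participant: GEE with robust SE and a small-sample correction (about 36 clusters), or a mixed model.
- Include categorical visit, the pre-RST score and treatment-type stratum. Define pre-RST as visit 0 for the intervention arm and visit 1 for controls, as the FOIS text already does.
- Report the change from pre-RST and the change from post-RST at 1, 3 and 6 months, each with a 95% CI.
- Base the durability conclusion on the retained change from pre-RST. It has no concurrent control after cross-over, so describe it as a within-person estimate.
- State that a non-significant post-RST versus follow-up difference will not be read as durability.
- In the Aim 2 text, name this model as the one for repeated MBSImP visits.

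The cost is a little more analysis work and a wording change. No new data or visits are needed.

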CASM will be applied to pre- and post-RST MBSSs to determine and visualize improvements in covariant swallowing mechanics resulting from RST and determine which of these treatments is predictive of swallowing improvement as measured by MBSImP and PAS scores. Following a Procrustes fit of coordinates to control for differences in size and image rotation, a canonical variate analysis with post hoc discriminant function analyses^{21,22} are performed to determine statistical differences in pre- and post-RST swallowing mechanics by phase of swallowing for each subject and the aggregate. Eigenvectors will be used to visualize differences in covariant swallowing associated with treatment effect. Morphometric regression analysis will be used to evaluate respiratory-swallow training as a predictor of improved swallowing outcomes as measured by MBSImP and PAS scores.

5.7 *Withdrawal of Subjects*

Participation is voluntary and the participant can withdraw from the study at anytime without penalty, consequences or loss of rights to which they are entitled. If the participant wishes to withdraw, they can contact study personnel at anytime. They will still receive compensation based on tasks completed as outlined previously. The investigator may withdrawal the participant from the study if they are unwilling or unable to follow study procedures or have worsening breathing problems, lung disease, or pneumonia.

6.0 **Reporting**

The PI ([name]) will be responsible for ensuring participant safety on a daily basis. An internal *Data and Safety Monitoring Board (DSMB)* - comprised of a radiation oncologist, medical oncologist, head and neck surgeon, pulmonologist, biostatistician, information technology specialist, and a speech-language pathologist - will act in an advisory capacity to monitor participant safety, evaluate the progress of the study, and to review procedures for maintaining the confidentiality of data, the quality of data collection, management, and analyses. The PI will be informed of serious adverse events as soon as they occur and will notify the IRB, DSMB, VA RR&D within 24 hours of notification. The *DSMB* will meet twice annually, either in-person or by teleconference call, to review study progress, data quality, and participant safety.

Safety reports will be sent to the PI twice a year and will include a detailed analysis of study progress, data and safety issues. *DSMB members* will have no direct involvement with the study investigators or intervention. Each DSMB member will sign a Conflict of Interest Statement regarding any relationship that could be perceived as a conflict of interest related to the study and/or associated with commercial interests pertinent to study objectives. Data will be presented in a blinded manner during the open sessions of the DSMB or in safety reports. Data and discussion will remain confidential during DSMB meetings and in safety reports. Participant identities will not be known to the DSMB members.

Any unanticipated problem, SAE, and/or protocol deviations will be immediately reported to the PI. All the SAE will be reported within Five working days of the Investigators Knowledge of the event to the Hines VA IRB. In the event when the PI is not able to continue to conduct the study, [name] (ENT) will take over the responsibilities as a PI.

7.0 Privacy and Confidentiality

This study will use subjects' Protected Health Information (PHI). Extensive efforts will be made by all study personnel to keep personal information and research records private and confidential. Each participant will be assigned an alphanumeric identifier (XX1, etc.), which will be used in lieu of other identifying information. All research related materials will be secure in a locked file cabinet at the Hines VA Hospital in Rm D326. Personal information will be given out as required by law. Only approved study personnel will be provided access, which requires appropriate VA and CITI training for research-related duties. A Certificate of Confidentiality will not be used for this study.

Study related data are stored on VA approved computers and the VA research shared drive (S:), including de-identified study-related data (videofluoroscopic images, respiratory traces). Identifiable data (VASA), including demographic data, questionnaire responses, and treatment results are stored on the VA REDCap behind the VA firewall. De-identified videofluoroscopic images and respiratory tracings will be transported via VA issued encrypted external hard drives for analysis by specially trained analytic experts to the PI's lab at Northwestern University, and then stored on and analyzed from a password protected, dedicated server. This server is managed by Northwestern Information Technology and accessible to only approved study personnel. We will update the data transfer and storage operations as we are provided additional guidance and requirements from the ORO, Office of Research Oversight.

Per VA regulations, research records, including identifiers will be destroyed 6 years after cutoff (at the end of the fiscal year) after completion of the research project, but may be retained longer if required by other federal regulations or sponsor archive requirement. Once a VA study personnel member leaves, his/her access to all data related to the study will be terminated. Prior to destruction of any research-related records, the PI will contact Records Management Officer for current policy.

8.0 Communication Plan

- Bi-monthly summary e-mail from Study Coordinator to review study progress and any items that need action.
- Routine monthly meetings via in person or via telephone conference call amongst all study personnel to discuss study progress and interpretation of study outcomes, as well as to identify and solve any barriers to study completion.
- Weekly bi-monthly meetings between Study Coordinator, Research SLP and PI, to discuss study progress and interpretation of study outcomes, with particular focus on study accrual, as well as to identify and solve any barriers to study completion.
- If there is a protocol deviation, serious adverse event, and/or unanticipated problem, the PI and IRB will be immediately notified. Additionally a summary of the event and solution with a plan to prevent future problems will also be communicated with all study personnel.
- Study Coordinator will routinely check for issues related to completion of IRB-approved study protocol, data collection and ensure the regulatory binder is up-to-date.

